15.1 Baseline Glycaemic Status

Individuals are classified as having diabetes remission status if all of the following is the satisfied:

- HbA1C <6.5%, not on glucose lowering medication and have a previous medical history of diabetes

Individuals are classified as having diabetes status if one of the following is the satisfied:

- HbA1C \geq 6.5%
- Have previous medical history of diabetes and they are on any glucose lowering medication (including Metformin)
- Are on any glucose-lowering medication except of Metformin (with or without past medical history of diabetes).

Individuals are classified as having pre-diabetes status if one of the following is the satisfied:

- HbA1C 6.0-6.4%, without a previous medical history of diabetes and not on any glucose-lowering medication.
- HbA1C 6.0-6.4%, without a previous medical history of diabetes and only on Metformin from glucose-lowering medications.
- HbA1C <6.0%, with a previous medical history of pre-diabetes (but without a previous medical history of diabetes) and only on Metformin from glucose-lowering medications.

Individuals are classified as having Normoglycaemia if one of the following is satisfied:

- HbA1C <6.0%, without a previous medical history of diabetes and not on any glucose-lowering medication.
- HbA1C <6.0%, without a previous medical history of diabetes or pre-diabetes and only on Metformin from glucose-lowering medications.

15.2 Follow-up Glycaemic Status

Individuals are classified as having diabetes remission status if all the following is satisfied:

- Follow-up HbA1C <6.5%, not on glucose lowering medication for \geq 3months, have a previous medical history of diabetes and have NOT being on LIRA 3mg within the last 3 months

Individuals are classified as having diabetes status if one of the following is the satisfied:

- Follow-up HbA1C \geq 6.5%
- Have previous medical history of diabetes and they are on any glucose lowering medication (including Metformin) within the last 3 months and/or have being on LIRA 3mg within the last 3 months
- Are on any glucose-lowering medication except of Metformin (LIRA 3mg is considered obesity medication, not glucose-lowering)

Individuals are classified as having pre-diabetes status if one of the following is the satisfied:

- Follow-up HbA1C 6.0-6.4%, without previous medical history of diabetes and not on any glucose-lowering medication (but they can be on LIRA 3mg).
- Follow-up HbA1C 6.0-6.4%, without previous medical history of diabetes and only on Metformin from glucose lowering agents (and they can also be on LIRA 3mg).
- Follow-up HbA1C <6.0%, with a previous medical history of pre-diabetes (but without a previous medical history of diabetes) and only on Metformin from glucose-lowering agents (and they can also be on LIRA 3mg).

Individuals are classified as having Normoglycaemia if one of the following is the satisfied:

- Follow-up HbA1C <6.0%, without a previous medical history of diabetes and not on any glucose-lowering medication (but they can be on LIRA 3mg).
- Follow-up HbA1C <6.0%, without a previous medical history of diabetes or pre-diabetes and only on Metformin from glucose-lowering medications (and they can also be on LIRA 3mg).

16 Appendix 9: Templates for Tables

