7.2 Inclusion Criteria

To be considered eligible to participate in this study, a patient must:

- be aged between 18-75 years old (inclusive)
- understand written and spoken English
- be able to give informed consent
- have a BMI ≥ 35 kg/m 2
- have been referred to the Tier 3 service in one of the participating sites
- have a stable body weight (less than 5kg self-reported change during the previous 12 weeks)
- have at least one of prediabetes, diabetes, hypertension, and/or obstructive sleep apnoea, as defined below:
 - prediabetes (defined as established diagnosis of impaired fasting glycaemia (IFG) from GP and/or established diagnosis of impaired glucose tolerance (IGT) from GP and/or HbA1C 42-47 mmol/mol (6-6.4%) without glucose lowering medications, at a blood test during the last 6 months)
 - diabetes (defined as established diagnosis of Type 2 diabetes from GP and/or HbA1C ≥ 48 mmol/mol ($\geq 6.5\%$) at a blood test during the last 6 months] and/or being treated with any combination of lifestyle, metformin, sulphonylureas, Thiazolidinediones (TZDs) or SGLT-2)
 - hypertension treated (defined as being on antihypertensive treatment with or without a diagnosis of hypertension from GP) or untreated (defined as Systolic Blood Pressure ≥ 140 mmHg at two consecutive visits at the Tier 3 clinic),
 - obstructive sleep apnoea (on CPAP or established diagnosis of Apnoea Hypopnoea Index ≥ 15 at sleep studies during the last 12 months).

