Epworth Sleepiness Scale	52, 104	Scored as per Appendix 3 as binary outcome for possible OSA or not with baseline values also presented
Epworth Sleepiness Scale	52, 104	Total score generated as per Appendix 3 with change from baseline analysed
Stop Bang questionnaire	52, 104	Scored as per Appendix 4 as no OSA (0-2), possible OSA (3-4), likely OSA (5-8) with baseline values also presented
Stop Bang questionnaire	52, 104	Total score generated as per Appendix 4 with change from baseline analysed
On CPAP	52, 104	Binary indicator of 1 if participant is on CPAP, 0 otherwise with baseline values also presented
Apnoea Hypopnoea Index for participants with sleep apnoea who cannot tolerate CPAP or for participants on fixed pressures CPAP	52, 104	Recorded as an integer in MACRO (AHI = sum of the number of apneas (pauses in breathing) plus the number of hypopneas (periods of shallow breathing) occurring on average, each hour.)
Oxygen desaturation index for participants with sleep apnoea who cannot tolerate CPAP or for participants on fixed pressures CPAP	52, 104	Recorded as integer in MACRO (The average number of desaturation episodes per hour can be measured using PSG and is called the oxygen desaturation index (ODI))
Obesity-related co-morbidities and their treatments (Prediabetes/Diabetes)		
Change in HbA1C from baseline (mmol/mol)	52, 104	Follow-up HbA1c – baseline HbA1c. Will be calculated for each Glycaemic Status separately as well as for all individuals, see Appendix 8 for Glycaemic Status definitions.

Change in HbA1C from baseline (%)	52, 104	Follow-up HbA1c – baseline HbA1c Will be calculated for each baseline Glycaemic Status separately as well as for all individuals, see Appendix 8 for Glycaemic Status definitions)
Glycaemic Status	52, 104	Individuals are classified as having Diabetes remission, Diabetes, Pre-diabetes or Normoglycaemia. The Glycaemic Statuses will be summarised overall as well as for each baseline Glycaemic Status separately. Appendix 8 has the definitions of Glycaemic Status at baseline and follow-up.
Number of agents for diabetes	52, 104	Change from baseline in the total number of medications taken for diabetes defined as medications in any of the following classes: metformin, sulphonylurea, thiazolidinedione, SGLT-2, GLP-1, and insulin.
Proportion of those with diabetes at baseline with HbA1C<7.0%	52, 104	From HbA1c measurement, a binary indicator will be derived, being 1 if participant achieves the target and 0 if they do not.

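### SAP 15.2 sets follow-up Glycaemic Status by recorded history, not baseline status, so the same change from baseline diabetes can get different labels

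*SAP*

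**What the plan says.** **Entry.** Protocol 7.2 admits diabetes by either of two routes: "diabetes (defined as established diagnosis of Type 2 diabetes from GP and/or HbA1C" of 48 mmol/mol (6.5%) or more in the last 6 months. A raised HbA1c is therefore enough.

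**Baseline status (SAP 15.1).** "Individuals are classified as having diabetes status if one of the following is the satisfied", and the first item on that list is HbA1c of 6.5% or more with no other condition. The third is "Are on any glucose-lowering medication except of Metformin (with or without past medical history of diabetes". HbA1c and medical history are separate items, and two of the three routes to baseline diabetes need no history.

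**Follow-up status (SAP 15.2).** Baseline status is not mentioned.
- Remission requires HbA1c below 6.5%, no glucose-lowering drug for at least 3 months, and that participants "have a previous medical history of diabetes and have NOT being on LIRA 3mg within the last 3 months".
- A participant with a history is classed as diabetes if on a glucose-lowering drug in the last 3 months "and/or have being on LIRA 3mg within the last 3 months".
- Normoglycaemia without drugs is "Follow-up HbA1C <6.0%, without a previous medical history of diabetes and not on any glucose-lowering medication (but they can be on LIRA 3mg").
- Normoglycaemia on metformin is "Follow-up HbA1C <6.0%, without a previous medical history of diabetes or pre-diabetes and only on Metformin from glucose-lowering medications", again with LIRA allowed.
- Pre-diabetes at HbA1c 6.0-6.4% likewise requires no history of diabetes and allows LIRA.

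**Reporting.** SAP 2.2.1 states: "The Glycaemic Statuses will be summarised overall as well as for each baseline Glycaemic Status separately". SAP 5.5.1 makes this outcome descriptive, without formal testing.

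**The concern.** The baseline classification accepts diabetes without a history, but the follow-up classification uses history to decide whether an improvement counts as remission. Participants who share one baseline category then fall under two sets of follow-up rules. The two sets also treat LIRA differently: recent use holds a participant with a history at diabetes, and is disregarded for one without.

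Improvement in prediabetes and diabetes is part of secondary objective 1. In the summary by baseline status, the baseline-diabetes group would show one and the same biochemical change as remission for some participants and normoglycaemia or pre-diabetes for others. The difference would reflect what was recorded at entry, not what happened to the participant.

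**Working it through.** The plan gives no figure to reproduce. The check applies the rules of SAP 15.1 and 15.2 literally.

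**Inputs.** The rules above, with one illustrative HbA1c per SAP band: 5.7% (below 6.0%), 6.2% (6.0-6.4%) and 6.8% (6.5% or more). Drug and LIRA use are taken over the last 3 months.

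**Step 1, baseline.** HbA1c 7.0% with no history of diabetes gives diabetes whether the participant takes no drug, metformin only, or another drug.

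**Step 2, follow-up, all combinations.** 3 histories (none, pre-diabetes, diabetes) × 3 HbA1c values × 3 drug states (none, metformin only, other) × 2 LIRA states = 54 cells.
- Without a history of diabetes: 2 × 3 × 3 × 2 = 36 cells, of which 0 give remission.
- With a history of diabetes: 1 × 3 × 3 × 2 = 18 cells, of which 2 give remission (HbA1c 5.7% and 6.2%, no drug, no LIRA).

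**Step 3, side by side.** All participants below had baseline diabetes and take no glucose-lowering drug at follow-up.

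| Follow-up HbA1c | LIRA within 3 months | Diabetes history recorded | No diabetes history recorded |
|---|---|---|---|
| 5.7% | no | remission | normoglycaemia |
| 5.7% | yes | diabetes | normoglycaemia |
| 6.2% | no | remission | pre-diabetes |
| 6.2% | yes | diabetes | pre-diabetes |

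In all four rows the label changes with history alone.

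**Step 4, related cases.**
- Metformin only, follow-up HbA1c 5.7%: diabetes with a diabetes history; normoglycaemia with no history of either condition.
- Baseline diabetes resting only on a non-metformin drug, without a history, meets the same problem once that drug is stopped.
- Prediabetes found by HbA1c only, on metformin only, follow-up HbA1c 5.7%: normoglycaemia. With a recorded history of pre-diabetes it is pre-diabetes.

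**Step 5, can history be read to include the entry finding?** The term is not defined. Protocol Appendix 3 marks medical history at screening only. Protocol 8.2 has it recorded at the visit where the HbA1c test is arranged, and 8.3.1 adds a participant questionnaire on medical history at baseline. Neither section says that a raised entry HbA1c becomes history, and SAP 15.1 lists the two separately. Changes in diseases are logged at later visits, but SAP 15.2 does not link that log to history.

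**The case against.** The strongest reply is that, at week 52, a previous history naturally includes diabetes established at entry. Protocol 8.6 speaks of past medical history required for inclusion, and HbA1c is an inclusion route. If the analyst works that way, the inconsistency disappears. This reading is possible, so remission is not strictly ruled out for these participants. But the SAP does not state it, the text of 15.1 points the other way, and two programmers could produce different tables.

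Second, Protocol 6.4.2 defines normoglycaemia from current HbA1c and drugs, with no history condition and no remission class. A drug-free participant with baseline diabetes and HbA1c now at 5.7% is normoglycaemic by that definition. This stands: the fault lies within the scheme that the SAP added, and a reader should not conclude that the label contradicts the protocol.

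Third, the consequences are limited. The outcome is untested. A table by baseline status would at least show moves from diabetes to normoglycaemia, although template 16.10 has no rows for that split. HbA1c targets for those with diabetes at baseline, and HbA1c change by glycaemic status, are reported without a follow-up history condition.

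Fourth, a reader might infer a bias between arms. The documents do not establish one. For participants without a history, the current text gives the same label on or off LIRA. The LIRA restriction binds only on those with a history, and only the intervention arm is assigned LIRA, so an effect by arm is possible. Its size and direction are unknown.

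**Conclusion.** The inconsistency is real on the literal text of SAP 15.1 and 15.2 and should be corrected. Participants with the same baseline status, follow-up HbA1c and treatment receive different labels according to recorded history. The conclusion assumes that previous medical history is not updated with the entry finding, which the SAP leaves open.

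Three stronger readings are not supported:
- **A head count.** A reader might assume that 30-40% of 392 participants have diabetes and that 5-15% of these were found by HbA1c only: 392 × 0.30 × 0.05 = 5.9 and 392 × 0.40 × 0.15 = 23.5, or about 6 to 24. Neither share is in the documents, and Protocol 8.10 speaks of a small number with diabetes. The sum also counts participants who do not improve and ignores HbA1c missing because of the pandemic halt to blood tests. The number affected cannot be derived.
- **Remission understated throughout.** This applies only to participants off LIRA and off glucose-lowering drugs for at least 3 months. Recent LIRA users would not count as remission under a consistent rule either.
- **A split by who had seen a GP.** The SAP's criterion is previous medical history, which it does not limit to GP records.

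The primary endpoint is unaffected.

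**What to change.** Add to SAP 15.2 that a previous medical history of diabetes includes a baseline Glycaemic Status of diabetes under 15.1, and that a previous medical history of pre-diabetes includes a baseline status of pre-diabetes. Apply this in every follow-up category. Baseline diabetes remission needs no mention, because 15.1 already requires a history for it.

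State the consequence beside the definition. Affected participants with HbA1c below 6.5% move as follows:
- off LIRA and off glucose-lowering drugs for at least 3 months: from normoglycaemia or pre-diabetes to remission;
- on LIRA within 3 months: to diabetes, as the SAP already does for those with a history;
- on metformin within 3 months: also to diabetes.

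The label for these participants will then depend on recent LIRA use, which it does not under the current text, so readers should be told.

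The change does not cover diabetes that arises after baseline and improves by week 104. One further sentence should say whether the log of disease changes counts as history.

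The cost is a wording change in SAP Appendix 8, using a variable already derived in 15.1 and no new data. The SAP is marked version 1.1 draft and is to be finalised before database lock.

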16.1 Disposition

Population	Control group (n =)		Intervention group (n =)		Total population (n =)	
	Number	Percentage	Number	Percentage	Number	Percentage
Complete cases						
Intention-to-treat						
Of whom, those who had bariatric surgery						
Per protocol						
Responder						

16.2 Protocol deviations

Type of protocol deviation	Control group (n =)		Intervention group (n =)		Total population (n =)	
	Number	Percentage	Number	Percentage	Number	Percentage
[TBC]						
[TBC]						
[TBC]						
[TBC]						

16.3 Summary of continuous baseline characteristics

Baseline characteristic	Control group (n =)						Intervention group (n =)						Total population (n =)			
	N missing	Mean	SD	Median	IQR	N missing	Mean	SD	Median	IQR	N missin	Mean	SD	Median	IC	
Age, years																
Weight, kg																
Body mass index, kg/m²																
Heart rate, beats/minute																
Waist circumference, cm																
HbA1c, mmol/mol																
HbA1c, %																
Albumin-creatinine ratio, mg/mmol																
Systolic blood pressure, mmHg																
Diastolic blood pressure, mmHg																
LDL cholesterol, mmol/L																

Baseline characteristic	Control group (n =)					Intervention group (n =)					Total population (n =)		
	N missing	Mean	SD	Median	IQR	N missing	Mean	SD	Median	IQR	missin	Mean	SD
HDL cholesterol, mmol/L													
Total cholesterol, mmol/L													
Triglycerides, mmol/L													
Average total MET-minutes/week													

Abbreviations: IQR, Interquartile Range; N, Number; SD, Standard Deviation.

16.4 Summary of categorical baseline characteristics

Baseline characteristic	Control group (n =)		Intervention group (n =)		Total population (n =)	
	Number	Percentage	Number	Percentage	Number	Percentage
Sex						
Men						
Women						
Missing						
Ethnicity						
[TBC]						
[TBC]						
[TBC]						
Missing						
Smoking status						
Never smoker						
Ex-smoker						
Current smoker						
Missing						
Glycaemic Status						
Normoglycaemia						
Prediabetes						
Diabetes						
Diabetes remission						
Missing						
Hypertension status						
No						
Yes						
Missing						
Sleep apnoea status						
No						
Yes						
Missing						
Total number of medications						
0						
1						

Baseline characteristic	Control group (n =)		Intervention group (n =)		Total population (n =)	
	Number	Percentage	Number	Percentage	Number	Percentage
2						
≥3						
Missing						
Number of diabetes medications						
0						
1						
2						
≥3						
Missing						
Type of diabetes medication						
SGLT-2						
Metformin						
Sulphonylureas						
Glitazones						
Missing						
Number of antihypertensive medications						
0						
1						
2						
≥3						
Missing						
CPAP use						
No						
Yes						
Missing						
Statin use						
No						
Yes						
Missing						

16.5 Comparison of continuous baseline characteristics between those with and without primary outcome data

Baseline characteristic	Missing primary outcome data (n =)				Non-missing primary outcome data (n =)				P-value ^a	
	N missing	Mean	SD	Median	IQR	N missing	Mean	SD	Median	
Age, years										
Weight, kg										
Body mass index, kg/m ²										
Waist circumference, cm										
Heart rate, beats/minute										
HbA1c, mmol/mol										
HbA1c, %										
Albumin-creatinine ratio, mg/mmol										
Systolic blood pressure, mmHg										
Diastolic blood pressure, mmHg										
LDL cholesterol, mmol/L										
HDL cholesterol, mmol/L										
Total cholesterol, mmol/L										
Triglycerides, mmol/L										

Trial: STRIVE
SAP Version: 1.1 DRAFT
Version Date: 01/08/2022

Baseline characteristic	Missing primary outcome data (n =)				Non-missing primary outcome data (n =)				P-value ^a	
	N missing	Mean	SD	Median	IQR	N missing	Mean	SD	Median	IQR
Average total MET-minutes/week										

Abbreviations: IQR, Interquartile Range; N, Number; SD, Standard Deviation.

^aP-values were estimated using a t-test for normally distributed variables and a Mann-Whitney test for non-normally distributed variables.

16.6 Comparison of categorical baseline characteristics between those with and without primary outcome data

Baseline characteristic	Missing primary outcome data (n =)		Non-missing primary outcome data (n =)		P-value ^a
	Number	Percentage	Number	Percentage	
Sex					
Men					
Women					
Missing					
Ethnicity					
[TBC]					
[TBC]					
[TBC]					
Missing					
Smoking status					
Never smoker					
Ex-smoker					
Current smoker					
Missing					
Glycaemic Status					
Normoglycaemia					
Prediabetes					
Diabetes					
Diabetes remission					
Missing					
Hypertension status					
No					
Yes					
Missing					
Sleep apnoea status					
No					
Yes					
Missing					
Total number of medications					
0					
1					

Baseline characteristic	Missing primary outcome data (n =)		Non-missing primary outcome data (n =)		P-value ^a
	Number	Percentage	Number	Percentage	
2					
≥3					
Missing					
Number of diabetes medications					
0					
1					
2					
≥3					
Missing					
Type of diabetes medication					
SGLT-2					
Metformin					
Sulphonylureas					
Glitazones					
Missing					
Number of antihypertensive medications					
0					
1					
2					
≥3					
Missing					
CPAP use					
No					
Yes					
Missing					
Statin use					
No					
Yes					
Missing					

^a P-values were estimated using a chi-squared test.

16.7 Analysis of primary outcome

Population	Control			Intervention			Adjusted difference between the two groups ^a	P-value
	N with data	N with outcome	% with outcome	N with data	N with outcome	% with outcome		
Complete cases^b								
Intention-to-treat								
Per protocol								
Responder								

Abbreviations: CI, Confidence Interval; OR, Odds Ratio.

^a Estimates are adjusted for the stratification variables: site and baseline body mass index ($\geq 45\text{kg}/\text{m}^2$; $< 45\text{kg}/\text{m}^2$).

^b Primary analysis

16.8 Analysis of secondary categorical anthropometric outcomes

Outcome	Control			Intervention			Adjusted difference between the two groups ^a	P-value
	N with data	N with outcome	% with outcome	N with data	N with outcome	% with outcome		
Weight loss of $\geq 5\%$								
16 weeks								
32 weeks								
52 weeks								
104 weeks								
Weight loss of $\geq 10\%$								
16 weeks								
32 weeks								
52 weeks								
104 weeks								
Weight loss of $\geq 15\%$								
16 weeks								
32 weeks								
52 weeks ^b								
104 weeks								
Maintenance of weight loss of $\geq 15\%$ among those								

Outcome	Control			Intervention			Adjusted difference between the two groups ^a	P-value
	N with data	N with outcome	% with outcome	N with data	N with outcome	% with outcome		
who lost $\geq 15\%$ at 52 weeks								
104 weeks								

Abbreviations: CI, Confidence Interval; OR, Odds Ratio.

^a Estimates are adjusted for the stratification variables: site and baseline body mass index ($\geq 45\text{kg}/\text{m}^2$; $< 45\text{kg}/\text{m}^2$).

^b Primary analysis.

16.9 Analysis of secondary continuous anthropometric outcomes

Outcome	Baseline		Follow-up		Change from baseline		Difference in change from baseline Adjusted mean difference (95% CI) ^a	P-value
	Control	Intervention	Control	Intervention	Control	Intervention		
Absolute weight (kg) at 16 weeks								
Number								
Mean							-	-
SD							-	-
Median							-	-
Range							-	-
Interquartile range							-	-
Absolute weight (kg) at 32 weeks								
Number								
Mean							-	-
SD							-	-
Median							-	-
Range							-	-
Interquartile range							-	-
Absolute weight (kg) at 52 weeks								
Number							-	-
Mean							-	-
SD							-	-

Outcome	Baseline		Follow-up		Change from baseline		Difference in change from baseline	Adjusted mean difference (95% CI) ^a	P-value
	Control	Intervention	Control	Intervention	Control	Intervention			
Median								-	-
Range								-	-
Interquartile range								-	-
Absolute weight (kg) at 104 weeks								-	-
Number								-	-
Mean								-	-
SD								-	-
Median								-	-
Range								-	-
Interquartile range								-	-
Relative change in weight (%) at 16 weeks								-	-
Number								-	-
Mean	-	-	-	-	-	-			
SD	-	-	-	-	-	-			
Median	-	-	-	-	-	-			
Range	-	-	-	-	-	-			
Interquartile range	-	-	-	-	-	-			
Relative change in weight (%) at 32 weeks								-	-
Number								-	-
Mean	-	-	-	-	-	-			

Outcome	Baseline		Follow-up		Change from baseline		Difference in change from baseline Adjusted mean difference (95% CI) ^a	P-value
	Control	Intervention	Control	Intervention	Control	Intervention		
SD	-	-	-	-	-	-	-	-
Median	-	-	-	-	-	-	-	-
Range	-	-	-	-	-	-	-	-
Interquartile range	-	-	-	-	-	-	-	-
Relative change in weight (%) at 52 weeks								
Number								
Mean	-	-	-	-	-	-	-	-
SD	-	-	-	-	-	-	-	-
Median	-	-	-	-	-	-	-	-
Range	-	-	-	-	-	-	-	-
Interquartile range	-	-	-	-	-	-	-	-
Relative change in weight (%) at 104 weeks								
Number								
Mean	-	-	-	-	-	-	-	-
SD	-	-	-	-	-	-	-	-
Median	-	-	-	-	-	-	-	-
Range	-	-	-	-	-	-	-	-
Interquartile range	-	-	-	-	-	-	-	-
Absolute BMI (kg/m²) at 52 weeks								
Number								

	Baseline		Follow-up		Change from baseline		Difference in change from baseline Adjusted mean difference (95% CI) ^a	P-value
	Control	Intervention	Control	Intervention	Control	Intervention		
Mean								
SD							-	-
Median							-	-
Range							-	-
Interquartile range							-	-
Absolute BMI (kg/m²) at 104 weeks								
Number								
Mean								
SD								
Median								
Range								
Interquartile range								
Absolute waist circumference (cm) at 52 weeks								
Number								
Mean								
SD								
Median								
Range								
Interquartile range								
Absolute change in waist circumference (cm) at 104 weeks								

Outcome	Baseline		Follow-up		Change from baseline		Difference in change from baseline Adjusted mean difference (95% CI) ^a	P-value
	Control	Intervention	Control	Intervention	Control	Intervention		
Number								
Mean							-	-
SD							-	-
Median							-	-
Range							-	-
Interquartile range							-	-

Abbreviations: BMI, Body Mass Index; CI, Confidence Interval; OR, Odds Ratio.

^a Estimates are adjusted for the stratification variables: site and baseline body mass index ($\geq 45\text{kg}/\text{m}^2$; $<45\text{kg}/\text{m}^2$).

